### 3 OVERALL DESIGN AND PLAN OF THE STUDY

#### 3.1 OVERVIEW

This is a phase II, multicenter, randomized, investigator-masked, 3-parallel groups, 7-week treatment duration in patients with OAG or OHT.

In this study approximately 126 patients (naïve patients or using ocular hypotensive medication) will be randomized.

The study duration will be 12 weeks.

A minimum of 4 visits and a maximum of 7 visits are planned. The number of visits will depend on the patient's screening status (naïve patients or patients using ocular hypotensive medication).

Randomized patients will attend 3 visits at the investigator center during the study treatment period:

- Visit #1: Screening visit:

At the end of the Screening visit:

- An eligible patient without ocular hypotensive medication (naïve patient) is randomized.
- An eligible patient using ocular hypotensive medication will undergo a washout period.

During the washout period, the patient may attend the following visits:

- Visit #1.1: Optional visit planned according to the investigator's judgement at any time during the washout period for intraocular pressure (IOP) monitoring
- Visit #1.2: Visit in case of extension of the washout period. If the IOP meets the entry requirement, visit is directly recorded as the Randomization visit (Visit #2 – D1).
- Visit #2 – D1: Randomization visit (Day 1)
  - For naïve patient this is the same day as Screening visit or in the 2 following weeks when the patient's eligibility is confirmed
  - For patient using a hypotensive medication before Screening visit, this is the day after the end of the washout period (with extension or not)

[figure not shown]
[figure not shown]
Only a patient screen failed at Visit #1 may be rescreened (1 time) with a new attributed patient number.

- Visit #3 – Week 2 (W2) - Day 15 ( $\pm 2$  days)
- Visit #4 – Week 4 (W4) - Day 29 ( $\pm 3$  days)
- Visit #5 – Week 7 (W7) - End of treatment visit, Day 50 ( $\pm 3$  days)

The investigator prescribes to the patient the best appropriate antiglaucoma treatment at the end of the Visit#5.

In case of premature study treatment discontinuation, the investigator prescribes to the patient the best appropriate antiglaucoma treatment and a visit should be scheduled as soon as possible and recorded in premature study treatment discontinuation visit.

Then the patient must perform all visits and study procedures planned until the Visit #5 (W7 visit).

[figure not shown]

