#### **4.4.3 Handling of patients after permanent study treatment discontinuation**

In the case of study treatment discontinuation, the investigator will prescribe the patient the best appropriate treatment if needed.

After study treatment is discontinued, the patient should perform the premature study treatment discontinuation visit as soon as possible. Then the patient must perform all planned visits and study procedures until the Visit #5 (W7 visit).

In all cases, the reason(s) and date of study treatment discontinuation must be recorded on the electronic case report form (e-CRF (End of treatment form) and patient files (source documentation). The patient must be followed up to establish whether the reason was an AE, and, if so, this must be reported in accordance with the procedures in [Section 6.2.3.1](#).

In the case of study treatment discontinuation, the investigator will prescribe the patient the best appropriate treatment if needed.

The patient discontinued for AE(s) will be followed up after discontinuation until the event is resolved or considered medically stable by the investigator.

Randomized participant who premature discontinue the study treatment must not be reincorporated.

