#### 6.2.3.13 Ocular tolerance assessment by the Investigator

The masked investigator has to answer to the following question:

*“Do you consider the ocular tolerance of the study treatment as?*

- Very satisfactory
- Satisfactory
- Not very satisfactory
- Unsatisfactory”.

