#### 6.2.3.15 Ocular symptoms immediately after drop instillation

The severity of ocular symptoms **immediately after drop instillation**: will be assessed by the masked Investigator (or masked delegates) asking the patient:

“Have you felt any ocular discomfort/unusual sensation IMMEDIATELY AFTER DROP INSTILLATION since the last visit?”

The following symptoms will be evaluated immediately after IMP instillation:

- Burning/irritation
- Stinging/Eye pain
- Itching/Pruritus
- Ocular redness
- Tearing
- Eye dryness feeling
- Foreign body sensation
- Blurred vision.

Severity will be assessed based on a 4-point scale:

- 0 = Absent,
- 1 = Mild, present but not disturbing
- 2 = Moderate, disturbing
- 3 = Severe, very distressing.

For each symptom, the usual duration and the frequency will be recorded. Frequency will be assessed as follows:

- Very often:  $\geq 80\%$  of instillation/administration
- Often:  $\geq 40\%$  et  $< 80\%$  of instillation/administration
- Not very often:  $\geq 10\%$  et  $< 40\%$  of instillation/administration
- Rarely:  $< 10\%$  of instillation/administration.

These procedures will be assessed globally for both eyes

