#### 6.2.3.17 Treatment compliance evaluation

Participant will receive a participant diary after the randomization. Each day from the first to the last IMP instillation participant will record in his/her participant diary:

- Date, time of IMP instillation and eyes instilled.

The patient will return all IMPs whether used or unused at each visit. The number of returned / unreturned IMPs will be recorded in the accountability log by the **unmasked team member**.

The **unmasked team member** will assess compliance by questioning the patient, checking the patient daily diary during the visit (e.g., if there was any treatment interruption or missed instillation) and by the number of used and unused IMPs.

The following information will be reported for each period in the e-CRF:

- Date and time of last IMP instillation
- Missed and daily dose modifications

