##### Ocular and systemic AEs

Ocular and systemic AEs reported during the study will be coded using the MedDRA dictionary.

Ocular and systemic AEs will be analyzed separately on the basis of the localization.

[figure not shown]
Summary tables will be performed on TEAEs. TEAEs are AEs that occurred after the first IMP instillation. AEs that occurred the day of the first IMP instillation will be reviewed during a blind review meeting to decide if they have to be considered as TEAE or not.

[figure not shown]
Separate descriptions of treatment-emergent ocular and systemic AEs will be performed by treatment group:

- Number and percentage of patients experiencing at least one AE, SAE, drug-related AE, and AE leading to premature study drug discontinuation

- Number and percentage of patients experiencing at least one AE, as well as the number of AEs, by SOC and PT. The same summary table will be performed for SAEs, drug-related AEs, drug-related SAEs and AEs leading to premature study drug discontinuation
- Number and percentage of patients with AEs, as well as the number of AEs, by SOC, PT, and severity
- Number and percentage of patients with AEs, as well as the number of AEs, by SOC, PT, and relationship with IMP.

Patient data listings will be provided.

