17.1. Ocular and Systemic Adverse Events

Ocular and systemic adverse events (AEs) will be coded using MedDRA central coding dictionary, Version 27.0 or higher. Ocular and systemic AEs will be analyzed separately on the basis of the localization [REDACTED]

A TEAE is defined as an AE that occurs or worsens in severity after at least one dose of IMP has been administered.

Document: ...\\Biostatistics\\Documentation\\SAP\\ T4090-201 Statistical Analysis Plan V1.0

Author: [REDACTED]

Version Number:

1.0

Version Date:

13Nov2024

Statistical Analysis Plan

Separate descriptions of treatment-emergent ocular and systemic TEAEs will be performed by treatment group:

- Number and percentage of patients experiencing at least one TEAE, serious TEAE, study treatment related TEAE, study treatment related serious TEAE, TEAE leading to study treatment discontinuation, TEAE leading to death, TEAE by maximum severity, and treatment-emergent adverse event of special interest (AESI - only for ocular AEs),
- Number and percentage of patients experiencing at least one TEAE, as well as the number of TEAEs, by SOC and PT. The same summary table will be performed for serious TEAEs, study treatment related TEAEs, study treatment related serious TEAEs, TEAEs leading to study treatment discontinuation, and treatment-emergent AESI (only ocular),
- Number and percentage of patients experiencing at least one TEAE, by SOC, PT, and maximum severity. The same summary table will be performed for study treatment related TEAEs,
- Number and percentage of patients experiencing at least one TEAE, by SOC, PT, and maximum relationship to study treatment.

Listings will include all AEs (TEAEs and non-TEAEs)

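### The TEAE definition has no limit after the last dose, so AEs arising off IMP can enter an arm's all-cause, severity, serious and AESI tables; add an on-IMP summary

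*SAP*

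**What the plan says.** **TEAE definition.** SAP 17.1: "A TEAE is defined as an AE that occurs or worsens in severity after at least one dose of IMP has been administered". Protocol 6.2.3.2 (Definitions) agrees in substance. Protocol 7.4.2 (Ocular and systemic AEs) is shorter: "TEAEs are AEs that occurred after the first IMP instillation". None of the three gives an end point tied to the last dose.

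**After stopping IMP.** Protocol 4.4.3: "Then the patient must perform all planned visits and study procedures until the Visit #5 (W7 visit". Protocol 3.1, 3.1.2 and 6.1.3 repeat the requirement. On replacement treatment, Protocol 3.1 says "the investigator prescribes to the patient the best appropriate antiglaucoma treatment and a visit should be scheduled as soon as possible", while Protocol 4.4.3 makes it conditional: "the investigator will prescribe the patient the best appropriate treatment if needed". Protocol 6.1.3 refers to continuity of antiglaucoma medication.

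**AE collection.** Under Protocol 6.2.3.5.1, AEs are collected from consent to the final study visit. For one further month they are reported only if the investigator knows of them and considers them caused by the IMP.

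**Tabulation.** SAP 5.5 assigns safety data to the treatment received. SAP 17.1 plans overview, SOC/PT, severity, serious, related and AESI tables of TEAEs. SAP 17 keeps safety descriptive. No table restricted to time on IMP is visible.

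**IMP-directed questions.** The Visit #4 and Visit #5 lists in Protocol 6.1.2 include the investigator's efficacy and tolerance ratings, the patient's tolerance rating, and symptoms after instillation. The wording is product-specific: "Do you consider the ocular tolerance of the study treatment as" (6.2.3.13) and "The following symptoms will be evaluated immediately after IMP instillation" (6.2.3.15).

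**The concern.** The three rules are each reasonable alone, but together they mix two periods. Take a patient who stops the IMP at Week 2, moves to another antiglaucoma treatment and has a new ocular AE at Week 5. That AE is a TEAE of the arm although no IMP was being used at onset.

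The mixing grows with the share of an arm that stops early. If the stopping rates of the two T4090 concentrations and Rhopressa differ, the all-cause tables of the three arms contain different amounts of off-IMP time. Protocol 3.3.2 lists TEAEs as safety and tolerability endpoints, and Protocol 3.2 says the data will be used to design Phase III. Readers will compare these tables across arms even though no test is planned.

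The secondary point concerns collection only. A patient off IMP since Week 2 cannot describe, at Week 7, symptoms after instilling the IMP since the previous visit.

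**Working it through.** The documents give no discontinuation rate and no AE rate, so there is no figure of the plan's own to reproduce. The check has two parts.

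**1. Which tables can contain off-IMP events**

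- *Entry:* onset after first dose (SAP 17.1). An AE off IMP qualifies.
- *Observation:* follow-up to Week 7 is required (Protocol 4.4.3) and AEs are collected to the final visit (Protocol 6.2.3.5.1). Such an AE will be seen. The exposed window runs from stopping to about Day 50.
- *Attribution:* treatment received (SAP 5.5). It counts for the arm.
- *Filter:* under Protocol 6.2.3.5, an AE clearly triggered by another treatment is Not related, and Related requires that other factors cannot reasonably explain it. A clear replacement-drug effect therefore leaves the related tables. An ambiguous ocular AE soon after a switch fits neither definition, yet one must be chosen.
- *Unfiltered:* the all-cause, severity and serious tables. The AESI table is also unfiltered, because Protocol 6.2.3.5.2 and SAP 17.1.5 select AESIs on significance, not relationship.

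**2. Size**

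Inputs: 126 patients randomised 1:1:1 (Protocol 4.5 and 7.5; SAP 3.2), so 126 / 3 = 42 per arm. Two quantities are assumed: *d*, the share of an arm that stops IMP, and *q*, the chance that a stopper not already counted has a new AE while off IMP.

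Extra TEAE patients per arm = 42 × *d* × *q*:

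| *d* | stoppers (42 × *d*) | *q* = 5% | *q* = 20% | *q* = 40% |
|---|---|---|---|---|
| 5% | 2.1 | 0.11 | 0.42 | 0.84 |
| 10% | 4.2 | 0.21 | 0.84 | 1.68 |
| 20% | 8.4 | 0.42 | 1.68 | 3.36 |
| 30% | 12.6 | 0.63 | 2.52 | 5.04 |

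As a share of the arm this is *d* × *q*: 0.10 × 0.20 = 2.0 percentage points and 0.20 × 0.20 = 4.0 points. Over the whole grid it runs from 0.25 to 12 points.

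These are upper bounds if *q* is applied to every stopper, because a patient already counted in the same row on IMP adds nobody. If half are already counted, 0.84 and 1.68 become 0.42 and 0.84. The overlap is complete in the overall any-TEAE row for patients who stopped because of a TEAE, so any effect from them appears in individual SOC/PT rows.

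Share of Day 1 to Day 50 follow-up spent off IMP, if all stoppers stop on day *s*, is *d* × (50 − *s*) / 49:

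- *d* = 10%: 0.10 × 35/49 = 7.1% (*s* = 15); 0.10 × 21/49 = 4.3% (*s* = 29)
- *d* = 20%: 14.3% and 8.6%

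This is a share of time, not of TEAE counts.

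The gap between 126 randomised and 120 evaluable (6/126 = 4.8%) cannot stand in for *d*. Under Protocol 4.1 a patient is evaluable with one dose and one complete post-randomisation IOP visit, so an early stopper can still be evaluable.

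**The case against.** Counting every AE after the first dose to the end of the study is an inclusive, conservative convention, and this is an exploratory pilot with descriptive safety tables. The plan also has safeguards. An AE clearly due to another treatment is classed Not related. Related and related serious TEAEs have their own tables. Reasons for stopping are presented (SAP 9.1), and TEAEs leading to discontinuation are tabulated (SAP 17.1.2). Listings of study day, medication and exposure (SAP 6.1, 13 and 15) would let a reader identify post-IMP events by hand. All of this stands. It limits the size and supports keeping the all-TEAE tables. It does not give a summary by arm of what happened while patients were using the product.

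Two stronger readings are tempting, and the documents do not support them.

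- *A reader might infer that replacement-drug effects are simply counted as effects of the randomised product, without end.* AE collection does end, the causality rule removes clear cases from the related tables, replacement is conditional in Protocol 4.4.3, and no passage says it is an eye drop.
- *A reader might infer that patients who stopped for intolerance will give good ratings at Week 7 and make a poorly tolerated product look well tolerated.* The SAP's analyses of tolerance, symptoms and investigator ratings are not visible, so how those ratings would be used cannot be checked. Protocol 4.4.2 also lists reasons for stopping other than intolerance. No figure for such a bias can be supported.

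The visit schedule table is not shown, and SAP 6.3 to 6.6 and parts of 5.5 and 17.1 are blacked out. A rule for off-IMP data may exist there; if so, the sponsor need only confirm it.

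**Conclusion.** The point holds in a limited form. On the visible text, AEs that arise off IMP can enter an arm's all-cause, severity, serious and AESI tables, and the related-TEAE tables separate them only as well as the causality judgement does.

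The effect is modest: at most about 0.8 to 1.7 extra TEAE patients per arm of 42 (2 to 4 percentage points), assuming that 10% to 20% stop and 20% of those have a new AE. Neither assumption comes from the documents. It would matter mainly if stopping rates differ between arms. This is a cheap improvement to the safety summary and does not undermine the planned tables.

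The secondary point is about collection only: no visible text exempts patients off IMP from questions that presuppose its use.

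**What to change.** **SAP 17.1.** Keep all planned TEAE tables. Add an on-IMP flag for TEAEs with onset from the first dose to the last IMP instillation plus a short window, fixed before unmasking. Repeat the overview and SOC/PT tables (all, related, AESI) on flagged events, and show later-onset AEs separately by arm. No new data are needed: the e-CRF already holds "Date and time of last IMP instillation" (Protocol 6.2.3.17), AE onset (6.2.3.5.1), the treatment discontinuation date (4.4.3) and concomitant treatment dates (5.2).

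**Protocol 6.2.2.2 and 6.2.3.13 to 6.2.3.15.** Unless text that is not visible already does so, allow 'not applicable' for the IMP-directed questions at visits after the premature discontinuation visit, and summarise the ratings given on IMP.

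**Protocol 3.1 and 4.4.3.** Reconcile the two statements on whether replacement treatment is conditional.

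**Cost.** One derived flag, a few repeated tables and one e-CRF response option. The downside is that a late-onset effect of the IMP would fall outside the on-IMP tables, which is why the all-TEAE tables must stay.

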17.1.1. All TEAEs

Incidence of TEAEs will be presented by SOC and PT and broken down further by maximum severity and maximum relationship to study treatment.

17.1.1.1. SEVERITY

Severity is classed as “mild”, “moderate”, and “severe” (increasing severity).

If a subject reports a TEAE more than once within that SOC/ PT, the AE with the highest severity will be used in the corresponding severity summaries.

17.1.1.2. RELATIONSHIP TO STUDY TREATMENT

Relationship, as indicated by the masked investigator, is classed as “not related”, and “related” (increasing severity of relationship).

If a subject reports the same AE more than once within that SOC/ PT, the AE with the worst-case relationship to study treatment will be used in the corresponding relationship summaries.

Document: ...\\Biostatistics\\Documentation\\SAP\\ T4090-201_Statistical Analysis Plan_V1.0

Author: [REDACTED]

Version Number: 1.0

Version Date: 13Nov2024

Statistical Analysis Plan

17.1.2. TEAEs Leading to Discontinuation of Study Treatment

A summary of TEAEs leading to discontinuation of study treatment by SOC and PT will be prepared.

17.1.3. Serious Adverse Events

A summary of serious TEAEs by SOC and PT will be prepared.

17.1.4. Adverse Events Leading to Death

The number of patients with TEAEs leading to death will be included in the overview TEAE summary table. The summary by SOC and PT will be part of the serious TEAE summary.

17.1.5. Adverse Events of Special Interest

Based on observations from previous studies with ROCKi, the following AEs will be considered as AESI, if judged significant by the investigator:

- All AEs related to CEC
- All AEs related to visual impairment (partial or total visual acuity loss)
- Corneal opacity
- Lens opacity/cataract
- Corneal verticillate

A summary of treatment-emergent (ocular) AESIs by SOC and PT will be prepared.

17.2. Deaths

If any subject dies during the study [REDACTED], the information will be presented in a data listing.

Document: ...\\Biostatistics\\Documentation\\SAP\\ T4090-201_Statistical Analysis Plan_V1.0

Author: [REDACTED]

Version Number: 1.0

Version Date: 13Nov2024
